4.2.4 Immunological data

The rules for handling BLQ or ALQ measurements for all immunological data will be as described in [Section 4.2.2](#).

Descriptive statistics will be calculated if at most 33% of the individual data points at a timepoint are missing or are either not quantifiable (<LLOQ) or ALQ as described in [Section 4.2.2](#).

4.2.5 Rozanolixizumab concentration data

Measurements that are BLQ will be imputed with half of the LLOQ for the purpose of calculating the geoMean and its 95% CI, the geoCV, the arithmetic mean, and SD for summaries

and figures. If any summary value (geoMean, arithmetic mean, lower CI level or minimum) is lower than LLOQ, then 'BLQ' will be displayed.

For the individual figures, any concentrations that are BLQ will be considered as missing, with the exception of predose BLQ measurements on Week 1/ Visit 2 for study participants treated with placebo in the parent study, which will be imputed with zero for linear scale plots.

Additional rules for PK data summaries are provided in Section 9.1.

4.2.6 Electrocardiogram data

For the ECG data, all calculations of changes from Baseline and descriptive statistics will be based on the mean of the triplicate assessments at each timepoint. If there are not 3 available measurements at a given timepoint, the mean will be calculated based on the number of measurements for which data is provided.

4.2.7 Dates and Times

Partial dates may be imputed for the following reasons:

- Classification of AEs as treatment-emergent
- Classification of medications and procedures as prior or concomitant
- Derivation of time to use of rescue medication

Imputed dates will not be shown in the listings; all dates will be displayed as reported in the database.

The following rules will be applied for partial start dates:

- If only the month and year are specified and the month and year of dosing is not the same as the month and year of the start date then use the 1st of the month, or the date of screening if this is later;
- If only the month and year are specified and the month and year of dosing is the same as the month and year of the start date, then use the date of dosing. If this results in an imputed start date that is after the specified end date, then use the 1st of the month, or the date of screening if this is later;
- If only the year is specified, and the year of dosing is not the same as the year of the start date then use January 01 of the year of the start date or the date of screening if this is later;
- If only the year is specified, and the year of dosing is the same as the year of the start date, then use the date of first dosing. If this results in an imputed start date that is after the specified end date, then use January 01 of the year of the start date, or the date of screening if this is later;
- If the start date is completely unknown, then use the date of dosing. If this results in an imputed start date that is after the specified end date, then use January 01 of the year of the end date, or the date of screening if this is later.

Missing start times will be imputed as 00:00h or with the time of dosing for events occurring on the date of IMP administration in case of missing hour and minute. Otherwise start times with only missing minutes will be imputed with :00.

Start and end time is not recorded for concomitant medications, thus no imputations for missing times will be performed. Any medication with a start date on the first dosing date, will be assumed to be concomitant.

The following rules will be applied for partial stop dates:

- If only the month and year are specified, then use the last day of the month;
- If only the year is specified, then use December 31 of the known year;
- If the stop date is completely unknown, do not impute the stop date

Missing or partially missing date and/or times will be imputed as described in [Table 4–1](#) for the calculation of duration of each AE. Adverse event duration is computed in and reported in day and time format: xx d hh:mm.

Table 4–1: Calculation rules for duration of AEs

Data availability	Onset date/time	Outcome date/time	Calculation rules
Complete data	D1/T1	D2/T2	Duration = $[(D2 - D1) * 24 + (T2 - T1)] / 24 \text{ d}$
End time missing	D1/T1	D2/--	End time is substituted by time 23:59h (=23.98 in decimal format) Duration = $<[(D2 - D1) * 24 + (23.98 - T1)] / 24 \text{ d}$
Start time missing	D1/--	D2/T2	Onset time is substituted by time 00:00h. Duration = $<[(D2 - D1) * 24 + T2] / 24 \text{ d}$
Start and end time missing	D1/--	D2/--	Duration = $<D2 - D1 + 1$
Start day and time missing	--/--	D2/T2	Duration = $<[(D2 - D0) * 24 + (T2 - T0)] / 24 \text{ d}$ For a study participant in the SS, D0 and T0 are the date and time of first administration of UCB7665 and for screen failures, D0 is the date of the screening visit and T0 = 00:00h

Table 4-1: Calculation rules for duration of AEs

Data availability	Onset date/time	Outcome date/time	Calculation rules
End day and time missing	D1/T1	--/--	
For ongoing AE: Duration = >Discharge day – D1 d OR Duration = >Data cut-off day – D1 d
 
For resolved AE: Duration = <Discharge day – D1 d OR Duration = < Data cut-off day – D1 d
 
Where discharge refers to the date of the end of study visit for completed study participants or the date of discontinuation for study participants that were withdrawn.
 
For any AEs with known start date/time after the date of discontinuation, the date of last contact will be used as the discharge day.
 
For study participants still ongoing in the study at the time of the data cut-off, and for whom no discharge date is available, the date of the data cut-off will be used instead of the discharge date.

Start and end date missing	--/--	--/--	
For ongoing AE: Duration = >Discharge day – D0 d OR Duration = >Data cut-off day – D0 d
 
For resolved AE: Duration = <Discharge day – D0 d OR Duration = < Data cut-off day – D0 d
 
For a study participant in the SS, D0 and T0 are the date and time of first administration of UCB7665 and for screen failures, D0 is the date of the screening visit and T0 = 00:00h.
 
Discharge refers to the date of the end of study visit or the date of discontinuation for study participants that were withdrawn.
 
For any AEs with known start date/time after the date of discontinuation, the date of last contact will be used as the discharge day.
 
For study participants still ongoing in the study at the time of the data cut-off, and for whom no discharge date is available, the date of the data cut-off will be used instead of the discharge date.

D0/1/2=Date0/1/2; T0/1/2=Time0/1/2; d=day.

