3.9 Changes to protocol-defined analyses

- CIDP relapse (maximum grip strength as assessed by site personnel) is defined as a clinically important deterioration from Baseline in grip strength as measured by site personnel, ie, a decline of $>14\text{kPa}$. Additionally, relapses defined by decline of $>8\text{kPa}$ will be investigated.
- The FAS definition is clarified to include at least one valid post baseline iRODS assessment result.
- The PD-PPS will be handled as a subset of the SS instead of the FAS as defined in the protocol to not exclude data due to missing efficacy results.
- To prevent bias in efficacy evaluation, an efficacy assessment is considered invalid, if that assessment follows the first intake of rescue medication. Assessments on the same day as first intake of rescue medication are considered valid.
- The MFAS is included as an additional analysis set in the SAP and was not part of the final clinical study protocol (CSP). This was added as a sensitivity analysis, to ensure the robustness of the efficacy results in relation to dose variation.
- Elevated liver function tests and potential drug induced liver injury criteria are harmonized across the rozanolixizumab program. Protocol-defined criteria are updated to match UCB's standard evaluations. Please refer to Section 10.3.1 for a list of the criteria that will be evaluated.

$\geq 3\times\text{ULN}$ ALT or AST with coexisting $\geq 2\times\text{ULN}$ total bilirubin in the absence of $\geq 2\times\text{ULN}$ ALP

will instead be defined as

(ALT or AST increase $\geq 3\times\text{ULN}$) and Total bilirubin $\geq 2\times\text{ULN}$ and ALP $<2\times\text{ULN}$ to match program standards and general medical definitions.

- The study variable “Change in CIDP-specific auto-antibody levels in serum from Baseline during Treatment and Observation Periods” will not be analyzed in scope of this SAP.

Sampling dates are captured in the CRF and will be listed. The samples’ results will not be part of this study’s database and instead analyzed and reported separately. The same is true for exploratory biomarkers RNA, proteins and metabolites variables.

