4.2 Handling of dropouts or missing data

4.2.1 Efficacy data

For study participants who prematurely withdraw for any reason before Visit 26, data collected during the PEOT Visit will be mapped to the closest missing visit according to the visit schedule utilizing the relative day in study to a maximum of Visit 26 (end of treatment period). However, if a participant receives rescue medication prior to the PEOT visit, any efficacy assessment post intake will be regarded invalid and only listed. Assessments on the same day as first intake of rescue medication are acceptable for analysis.

Study participants administered an Ig infusion rescue medication during the treatment phase will be considered relapsed even in case no relapse was documented. Missing relapse data, i.e. data for any relapse event definition, will be considered missing. In case of drop-out, if no relapse occurs or rescue medication is taken until PEOT visit (inclusively), the subject will be censored for time-to-event analysis at the date of PEOT visit.

Participants are asked to record three grip strength score assessments at each day. The efficacy parameter will be derived from grip strength scores taken by a participant up to five days prior to the first IMP (for Baseline value) or visit date (for post Baseline visit value):

1. Maximum of grip strength assessments available at a particular day
2. Mean of maximum grip strength over most recent three non-missing days - up to a maximum of five days
3. Missing values: In case all three assessments of a day are missing, the maximum grip strength score will be set to missing and will not be used for the derived score. In this case the preceding day's maximum grip strength score will be used instead, but no later than the fifth day prior to the first IMP or visit date respectively. In case data is entirely missing during the last five days prior to the visit, the derived score will be set to missing.

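### SAP 4.2.7 dates an incompletely recorded rescue with rules suited to adverse-event classification, so a year-only or unknown date can fall at first dosing and contradict infusions recorded later

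*SAP*

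**What the plan says.** SAP 4.2.7 allows partial dates to be imputed for three purposes: deciding whether an adverse event is treatment-emergent, classifying medications and procedures as prior or concomitant, and "Derivation of time to use of rescue medication". One set of start-date rules serves all three:

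- Day missing, month different from the dosing month: "then use the 1st of the month, or the date of screening if this is later".
- Day missing, same month: "month and year of dosing is the same as the month and year of the start date, then use the date of dosing".
- Only the year known, same year as dosing: "the year of dosing is the same as the year of the start date, then use the date of first dosing". If the year differs, 1 January of the recorded year (or the screening date if later).
- Nothing known: "If the start date is completely unknown, then use the date of dosing".

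Where the dosing date would fall after the recorded end date, an earlier fallback applies. Imputed dates do not appear in the listings.

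SAP 8.5 takes time to rescue from the relative day of the first rescue and adds no date rule. Three other provisions depend on when rescue happened. SAP 4.2.1 says "Study participants administered an Ig infusion rescue medication during the treatment phase will be considered relapsed even in case no relapse was documented", and SAP 8.1.2 treats rescue as relapse in the time-to-event analysis. SAP 3.9 says that "an efficacy assessment is considered invalid, if that assessment follows the first intake of rescue medication"; same-day assessments remain valid. SAP 3.5.3 requires a valid post-Baseline iRODS for entry to the Full Analysis Set (FAS).

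**The concern.** Moving an uncertain start date back to first dosing is cautious when the question is whether an event arose on treatment. For a time-to-event efficacy variable the same move makes the event too early, in some cases by months.

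It can also contradict the trial's own records. Protocol 6.4 requires permanent discontinuation of study drug after rescue, and 7.8.3 links rescue to withdrawal from it. A participant with infusions recorded after the first one was therefore not rescued on the first dosing day unless the protocol was breached. Those infusion and visit records would give a better date, and the rule does not use them.

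The rule also sits awkwardly with Protocol 14.6. That section leaves partial dates for safety assessments to the SAP and rules out imputing missing efficacy data for participants who withdraw early. SAP 3.9 does not list the extension to rescue as a change.

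At stake is the time-to-rescue analysis. Relapse timing and the set of valid efficacy assessments are also affected if the imputed date is used there.

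**Working it through.** The plan gives no figure to reproduce, so the 4.2.7 rules were applied to rescues whose true date is known.

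**Inputs from the documents:** the rules above; Day = event date − first infusion + 1 (SAP 3.2.1.1); post-Baseline iRODS at Weeks 2, 3, 4, 5, 7, 9, 13, 17, 21 and 25, then every 4 weeks (Protocol Table 5-1); treatment to Week 76 at most.

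**Assumptions:** newly treated participant, first dose 10 Feb 2020, no stop date recorded, *date of dosing* read as first dose.

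**Main example.** Rescue on 20 Aug 2020, recorded as 2020. From 10 Feb to 20 Aug: 19 + 31 + 30 + 31 + 30 + 31 + 20 = 192 days, so the true day is 193. The year matches the dosing year, so the imputed day is 1, which is 192 days early.

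The last column holds only if the imputed date also sets the validity cut-off.

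| True day | Recorded | Imputed day | Days early | Valid iRODS visits, true → imputed |
|---|---|---|---|---|
| 18 | month, year only, or nothing | 1 | 17 | 2 → 0 |
| 60 | month | 52 | 8 | 6 → 5 |
| 116 | month | 113 | 3 | 8 → 8 |
| 116 | year only, or nothing | 1 | 115 | 8 → 0 |
| 193 | month | 174 | 19 | 10 → 10 |
| 193 | year only | 1 | 192 | 10 → 0 |
| 417 | year only | 327 (1 Jan 2021) | 90 | 18 → 15 |
| 417 | nothing | 1 | 416 | 18 → 0 |

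**Averages in Part 1.** First doses were spread evenly over 1 Jul 2019 to 29 Jun 2020 and true rescues over Days 2 to 168:

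- Month-only: mean 13.9 days early, maximum 30; Day 1 in 8.9%.
- Year-only: mean 71 days early, maximum 167; Day 1 in 77%.
- Unknown: mean 84 days early, maximum 167; Day 1 in 100%.

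**Which dose?** SAP 3.2.1.1 counts days from the CIDP01 first infusion for previously treated participants. Assume that infusion came 84 days before CIDP04 entry. A rescue on Day 200 with an unknown date then goes to Day 1, before CIDP04 began, if the CIDP01 dose is meant. It goes to Day 85 if the CIDP04 first dose is meant. The text does not say which.

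**Can a false early event and loss from the FAS both occur?** For a newly treated participant, if the imputed date sets the cut-off, Day 1 leaves no valid post-Baseline iRODS. The participant leaves the FAS, and because efficacy summaries use the FAS (SAP 8), the Day 1 event is not counted. If the date does not set the cut-off, the participant stays and the false event counts. A previously treated participant imputed to the CIDP04 first dose has a valid same-day Visit 2 iRODS that is already post-Baseline (SAP 3.3), so remains in the FAS with the early event.

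**The case against.** Four counter-arguments deserve weight.

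*Incomplete rescue dates should be rare.* Concomitant medication is collected at weekly visits, rescue is flagged in the eCRF, and stopping study drug triggers a premature-end-of-treatment visit. This stands and keeps the point minor. The documents give no expected count.

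*Not every incomplete date becomes Day 1.* A reader might infer that it does. The text does not support that: a month-only date moves by at most 30 days and reaches the dosing date only in the dosing month. The rule for a wholly unknown date does not say first dosing at all.

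*Loss of efficacy data is not stated.* A reader might conclude that the rule wipes out efficacy data preceding the real rescue. The purposes listed in 4.2.7 include neither relapse timing nor validity, and the validity rules speak of actual first intake. SAP 4.2.1 also says missing relapse data stay missing. That consequence is conditional, and the SAP leaves the condition open.

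*An early failure date is conservative against the drug.* This is true of the event time taken alone. It need not hold overall: if the same date sets validity, a rescued newly treated participant drops out of the FAS, which removes a failure. Nor does conservatism justify a date that the dosing record contradicts. Imputing to the latest possible date would be no better: for 2020 it gives 31 December, 133 days after 20 August.

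**Conclusion.** The point holds in a limited form. SAP 4.2.7 explicitly applies to time to rescue a rule that places year-only dates (in the dosing year) at first dosing and unknown dates at an undefined dosing date. Read as first dosing, the result contradicts any later recorded infusions. This is a stated rule that gives a wrong value, not merely missing detail.

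The size per affected record is at most 30 days for a month-only date, 192 days in the year-only example, and 416 days for an unknown date with rescue in Week 60. These figures rest on the assumed first-dose date, on no recorded stop date, and on *date of dosing* meaning first dose.

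Two stronger readings are not supported. The SAP does not say that imputed rescue dates invalidate earlier assessments or set relapse time; it leaves both open. For a newly treated participant, a false Day 1 event and loss from the FAS cannot both follow from one record. Because incomplete dates should be few, the change is desirable rather than essential.

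**What to change.** In SAP 4.2.7, remove rescue from the general start-date rule and add a separate one:

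- **Lower bound:** the later of the last dose of study drug and the last visit with no rescue recorded.
- **Upper bound:** the earliest of the first visit recording rescue, the rescue stop date, and the end of the known month or year.
- **Imputed date:** the documented relapse date if it lies within the bounds, otherwise the day after the lower bound. Never default to first dosing.
- **Use:** state that this same date sets relapse time and the validity cut-off. Assessments up to the lower bound then stay valid, and those after the imputed date are only listed.
- **Definition:** say whether *date of dosing* means the first dose in CIDP01 or in CIDP04.

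In the main example, suppose the last infusion and the last rescue-free visit were both on 17 Aug 2020 and no relapse date was documented. The imputed date is then 18 Aug (Day 191), 2 days early instead of 192, and all 10 scheduled iRODS visits stay valid.

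The cost is a few sentences and a small derivation from data already collected.

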4.2.8 Handling of repeated and unscheduled measurements

All repeated and unscheduled measurements will be presented in the listings where applicable. The following general rules will apply to all repeated and unscheduled measurements:

- For repeated or unscheduled measurements obtained prior to dosing the latest value (which may be scheduled or unscheduled) will be used in the calculation of the descriptive statistics at each visit (ie, Screening and/or Baseline);
- For repeated or unscheduled measurements obtained at the designated Baseline visit, the latest value (which may be scheduled or unscheduled) will be defined as the Baseline provided that the measurement occurred prior to dosing;
- For repeated or unscheduled measurements taken at any timepoint after dosing, the first original value (if non-missing) will be used in the calculation of changes from Baseline and for the descriptive statistics (ie, in summaries by timepoint). Unscheduled and repeated measurements will generally not be included in summaries by timepoint after dosing.

The above rules also apply to triplicate measurements obtained for the ECG data.

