8.6 Unscheduled Visit/Telephone call

At any time, a study participant may have an unscheduled study visit/telephone call if the investigator and/or the study participant deem it necessary. An unscheduled visit may be conducted due to safety or efficacy reasons and appropriate assessments will be conducted in relation to the reason for the visit. All information, including reason for visit, any information on AEs, etc, should be collected in the source documents and recorded in the appropriate section of the eCRF.

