14.3 Planned safety analyses

14.3.1 Safety analyses

The incidence of study participants with TEAEs will be determined. Furthermore, the absolute and relative frequencies for study participants with a given TEAE with respect to the preferred term according to the latest available version of the Medical Dictionary for Regulatory Activities

(MedDRA®), will be determined within each system organ class. Additional tables will summarize TEAEs by maximum severity and causal relationship with rozanolixizumab, as judged by the investigator. Adverse events will be categorized by severity according to the National Institutes for Health CTCAE version 5.0 grading (National Institutes for Health, 2017). In case the CTCAE grading is not available, the intensity (mild/moderate/severe) will be utilized. The TEAEs leading to discontinuation of IMP and the serious TEAEs will also be summarized. The action taken, time of onset relative to dosing, actual dose received, and duration of each AE will be listed only.

For the continuous laboratory variables, the values and changes from Baseline will be descriptively summarized at each time point. For categorized values according to the reference range, shift tables from Baseline to each post-Baseline time point will be presented for selected variables to be defined in the SAP. Values outside the reference range will be flagged in the data listings.

Descriptive statistics will be presented for ECG value and changes from Baseline over time based on the mean of the triplicate assessments at each time point. Categorical analyses for QTc, eg, QTc increase >60msec, will also be performed.

Descriptive statistics will be reported for all vital sign measurements (including BP, PR, temperature, and body weight). Measured values and changes from Baseline will be summarized by time point.

Physical and neurological examination findings and the results of any pregnancy testing will be presented in listings only. Results will be listed for any study participants who complete a headache questionnaire, undergo stool sampling, or lumbar puncture, etc.

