10.4.2 Electrocardiograms

Standard 12-lead ECG recordings will be taken in triplicate with the study participant resting in the supine position for at least 15 minutes and before obtaining any blood samples for assessments of laboratory variables. The following variables will be reported:

- Heart rate
- RR interval
- PQ/PR interval
- QRS duration
- QT interval

- QT corrected for heart rate using Fridericia's formula ($QTcF = QT / \sqrt[3]{RR}$)

The individual measurements and the mean of the triplicate measurements will be reported in the by-study participant listings. The listing will also include the change from Baseline (based on the mean of the triplicate measurements at each timepoint) and will be presented by treatment group and by timepoint. The listing will also include a flag for values identified as MA as defined by the criteria outlined in [Section 13.2](#)**Error! Reference source not found.**

Summarization will be as treated, study participants who missed treatments will not be summarized.

Measured values and changes from Baseline will be summarized by treatment group at each timepoint and by ECG variable (based on the mean of the triplicate values at each timepoint).

The following cut-points in QTcF (raw data and change from Baseline) will be summarized categorically by treatment group (number and percentage of participants) and visit/timepoint. The denominator for the percentages will be the number of participants with a non-missing measurement for the variable at the specific visit/timepoint.

Raw QTcF data:

- <450msec
- ≥450msec to <480msec
- ≥480msec to <500msec
- ≥500msec

Change from Baseline QTcF:

- <30msec
- ≥30ms to <60msec
- ≥60msec

Electrocardiogram findings for the individual triplicate measurements will be listed separately.

Repeated and unscheduled measurements will be handled as described in [Section 4.2.8](#).

In the event that the complete set of triplicate measurements is not available at a specified timepoint the data will be handled as described in [Section 4.2.6](#).

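### A QTcF outlier on an unscheduled ECG is listed and flagged but enters no summary count; whether unscheduled scores feed the relapse derivation is left unsaid

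*SAP*

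**What the plan says.** SAP 4.2.8 sets one rule for extra measurements of every kind. Before dosing, the latest value is used. After dosing, "the first original value (if non-missing) will be used in the calculation of changes from Baseline and for the descriptive statistics", with a gloss in the same sentence that refers to by-timepoint summaries, and then "Unscheduled and repeated measurements will generally not be included in summaries by timepoint after dosing". It adds that "The above rules also apply to triplicate measurements obtained for the ECG data". It also says "All repeated and unscheduled measurements will be presented in the listings where applicable".

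SAP 10.4.2 tabulates QTcF value and change categories by treatment group and visit or timepoint. "The denominator for the percentages will be the number of participants with a non-missing measurement for the variable at the specific visit/timepoint". It points back to 4.2.8 for repeated and unscheduled readings and plans no row for the worst value after Baseline. Markedly abnormal values are flagged in the ECG listing; SAP Table 13-2 sets the QTcF limits at 500 ms or more and an increase of 60 ms or more.

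Protocol 14.3.1 promises that "Categorical analyses for QTc, eg, QTc increase >60msec, will also be performed". Protocol 8.6 allows extra visits: "An unscheduled visit may be conducted due to safety or efficacy reasons and appropriate assessments will be conducted".

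For relapse, SAP 8.1.2 to 8.3.3 define each score criterion as a change from Baseline, and 8.4 combines them. None of these sections says whether scores from unscheduled visits are inputs.

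**The concern.** Leaving extra readings out is sensible for means by visit: it keeps one value per participant per visit and avoids giving more weight to people who are examined more often. It suits a count of participants who ever crossed a safety limit less well. An ECG taken because of symptoms is more likely than a routine one to be extreme, and a by-visit table has no place for it. The readings most relevant to the outlier count are then the ones outside it.

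The relapse analyses raise a related question. Each criterion is a change from Baseline, which is the quantity that 4.2.8 restricts, yet relapse is an event that the protocol lets the investigator look for at any time. If programmers apply 4.2.8 literally, a score taken at a visit arranged because the participant was worse might not be used. At stake are the criterion-specific relapse proportions and the Kaplan-Meier event dates.

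**Working it through.** The plan states no figure on this point, so the check traces the rule through the sections that use it.

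**1. Scheduled ECGs** (Protocol Table 5-1, sections 8.2 to 8.4). In Part 1 they are frequent: Visits 2 to 5, Visit 8, then every two weeks from Week 9 to Week 23. In Part 2 they fall at Weeks 25, 37, 49 and 61, and the next is Visit 26 at Week 77 for a participant who completes Part 2. Gaps in weeks: 37 − 25 = 12; 49 − 37 = 12; 61 − 49 = 12; 77 − 61 = 16. An ECG done for symptoms inside one of these gaps is unscheduled unless it is part of a PEOT visit.

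**2. What happens to a QTcF outlier** under 4.2.8 and 10.4.2 together:

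| Situation | In the QTcF table? | In the listing? |
|---|---|---|
| Scheduled ECG crosses a limit | Yes | Yes, flagged |
| Scheduled ECG crosses a limit and is repeated | Yes, on the original value | Both values |
| Scheduled ECG is below the limit; its repeat crosses | No, the original value is used | Yes, flagged |
| Stand-alone unscheduled ECG crosses | No, it has no visit row | Yes, flagged |

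The third and fourth rows are the gap, and the fourth is the main one. The word generally in 4.2.8 would permit an exception, but no criterion for one is given. The non-missing proviso matters only when the original reading is absent.

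**3. Other sections.** SAP 9.2.1 takes each participant's IgG minimum from all available data. SAP 10.3.1 counts liver criteria met at whichever visit, although it does not say that unscheduled samples are included. QTcF has no summary of either kind.

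**4. Relapse: which routes still count the event?**
- Immunoglobulin rescue during treatment counts as relapse even if none was documented (SAP 4.2.1). SAP 8.1.2 repeats this for iRODS, and 8.2.2, 8.3.2 and 8.3.3 take over the same methods for INCAT and both grip thresholds.
- Scores up to and including the day of first rescue stay valid, and PEOT scores are mapped to the visit schedule (SAP 4.2.1). Protocol 8.5 places PEOT as near as possible to the withdrawal decision.
- A relapse that the investigator records under the other category enters the composite (SAP 8.4), but not the single-criterion analyses.

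What remains is a crossing at an unscheduled visit, with no immunoglobulin rescue, that is not reproduced at PEOT.

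**5. Delay if such a crossing is picked up at the next scheduled score.** From Week 9 the scores fall at Weeks 9, 13, 17 and 21 (4 visits) and every four weeks from 25 to 73 (13 visits): 4 + 13 = 17 of the 68 weeks from 9 to 76, leaving 68 − 17 = 51 without a scheduled score. On this weekly grid, a crossing in Weeks 10 to 12 would be dated to Week 13, which is 13 − 12 = 1 to 13 − 10 = 3 weeks late. A prompt PEOT shortens that.

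**The case against.** The strongest reply is that this is a descriptive single-arm extension with full listings. The protocol defines the ECG variable at scheduled assessments (section 4.1.2), the promised categorical QTc analysis is delivered, and no any-time row was promised. The primary safety variable is the occurrence of TEAEs, which 4.2.8 does not touch. In Part 1 the scheduled ECGs are dense. All of this stands, and it limits the weight of the point. It does not remove the gap, because a flag in a listing is not a count.

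Three stronger readings are tempting, and the documents do not support them.
- A reader might infer that repeating an abnormal ECG removes the abnormality from the table. The opposite holds: the original value is kept, so the reading that prompted the repeat is counted.
- A reader might infer that a score-defined relapse at an unscheduled visit is never counted. The post-dose rule is glossed as concerning by-timepoint summaries, and relapse is an event up to Week 25 or Week 77 rather than such a summary. SAP 8.1.2 also censors ongoing participants without relapse at their last available assessment, not their last scheduled one. Rescue, PEOT and the other category each provide a further route.
- A reader might take 51 of 68 weeks (75%) as a rate of lost relapses. It is only the share of calendar weeks without a scheduled score; home visits may also be changed to site visits.

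**Conclusion.** The QTcF point holds. As written, an outlier on a stand-alone unscheduled ECG reaches the flagged listing and no planned summary count; the same applies when a repeat crosses a limit that the original did not. Its effect on the outlier count can only be to understate it. The size cannot be given: the documents state no rate of unscheduled ECGs, and the planned number of participants is blacked out in the public copy. The exposure is greatest in Part 2, where scheduled ECGs are 12 to 16 weeks apart.

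The relapse point is secondary and is an ambiguity rather than an exclusion. It could lose or delay an event for one criterion only where there is no immunoglobulin rescue and the crossing is not reproduced at PEOT. This rests on 4.2.8 being applied to the relapse derivation, which the SAP neither states nor rules out.

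The change is worth making before database lock, because it improves a safety count and removes a programming choice at little cost.

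**What to change.** - **SAP 10.4.2:** add an any-time post-Baseline row for both the QTcF value and the QTcF change categories, using each participant's highest triplicate mean and including unscheduled and repeat ECGs. The denominator would be participants with at least one post-Baseline ECG. Keep the by-visit table as it is.
- **SAP 4.2.8:** state that the post-dose rule governs by-timepoint descriptive statistics only.
- **SAP 8.1.2 to 8.4:** state that relapse by each criterion, and its date, use all valid assessments after the first dose, scheduled or unscheduled. The existing rule on validity after rescue is unchanged.

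The cost is one more table row and a few lines of SAP text and programming; no new data are needed. The downside is a few extra looks at the relapse thresholds for participants seen more often, which the report should mention.
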